**Consent/No consent:**

As the app opens, the care staff will obtain verbal consent (resident uses affirming, positive words or sounds) or non-verbal consent (resident smiles/nods/leans toward the tablet/touches care staff in a positive way/agrees to touch the screen either independently with care staff's support).

If no consent, the caregiver will reapproach in 3-5 minutes, again check if the

person is comfortable, and make any adjustments to improve comfort. Care staff will seek consent again. If consent is not given a second time, the DWS will be dropped and the usual ADL routine will begin.

**Ongoing Participation or Refusal:**

Staff will record the resident's attitude to the DWS in their daily report. The research team will review these reports daily.

Refusal may be communicated verbally (using negative or anxious words or sounds) or non-verbally (shrugging, shaking head, pushing the tablet away, refusing to put hand to the tablet, not permitting the care staff to hold their hand to support screen tapping, turning their body away, looking away from the app, passive disinterest

If a resident-participant decides that they no longer want to be involved in the study, not just the DWS session for the day, they will be offered DWS sessions daily. After 7 consecutive days of refusals, they will be withdrawn from the study.

(Guidance on the Process Consent method is covered during training and is described below.)

- Plan for 5 mins per session
- Upon consent, care staff initiates the DWS and guides the resident to the part of DevaWorld where the interactive ADL will be explored
- Following the resident's lead in pace and interest, the dyad focuses on helping the DevaWorld characters (male or female) to manage self-care activities in DevaWorld's bathroom and getting him/her ready for bed.
- The session will end when the resident seems ready
- Upon completion of a session, the care staff assists the resident, if needed, to select an emoticon on the end screen before ending the DWS.
- After completing the DWS, the care staff will initiate the planned ADL task, and observe their resident's interactions, cooperation, mood and any behavioral responses.
- Process Consent (21). This method is used during DevaWorld sessions.
  - Staff participant checks consent prior, during and after DW session.  
If Subject indicates their withdrawal of consent, Staff stops and lets the resident withdraw before or during the activity
  - If the resident no longer wants, or is no longer able, to be involved.  
The staff observes residents wishes (verbally or non-verbally) to guide the next steps. Staff then informs the researcher.
  - Depending on the situation, it may or may not be appropriate to ask the resident again later if they would like the opportunity to get involved., The caregiver will reapproach in 3-5 minutes, again check if the person is comfortable, and make any adjustments to improve comfort. Care staff will seek consent again. If consent is not given a second time, the DWS will be dropped and the usual ADL routine will begin.
- Assessments, tools  
Reliability  
A staff champion (internal) will be appointed to oversee adherence to the study and liaise with the research team about any obstacles they notice along the way, such as

absenteeism or the need for extra training. A research assistant (external), in the role of reliability observer, will be assigned to track data, checking for reporting compliance and anomalies. The PI will review data week-by-week to ensure the study design continues to fit its purpose.

- Data collected at Baseline

Residents

- **Demographic variables:** Gender, age, race, ethnicity, marital status, socioeconomic status, languages spoken/language preference.
- **Stage of dementia** The Global Deterioration Scale for Assessment of Primary Degenerative Dementia (GDS) (16)
- **Cognitive Function:** The Mini Mental State Exam (MMSE) (20).
- **Functional stage** (Functional Assessment Staging Tool (FAST), (22): The FAST is used to describe the stages of dementia and employs a seven-stage system based on one's level of functioning and ability to perform daily living activities.
- **Time since admission** to facility (in months) {subtract date of admission from date of assessment).
- **Quality of life:**  
-DEMQOL/DEMQOL-proxy (23).
- **Response Behaviors**  
- The Neuropsychiatric Inventory (NPI): Assessing psychopathology in dementia patients. (24).
- **ADL capacity**  
Alzheimer's Disease Cooperative Study Activities of Daily Living Inventory (ADCS-ADL) 19- item inventory to assess activities of daily living for clinical trials in Alzheimer's disease. (25).

Care Staff

- **Demographics:** Age, gender, race, ethnicity, number of years of schooling and highest degree obtained, US or foreign born; languages spoken/language preference, marital status, currently or previously the primary informal caregiver of a person with dementia (a predictor of job satisfaction (26). Job background: Years as a CNA, years working for this employer, employed full or part time.
- **Burnout:** Copenhagen Burnout Inventory (27).
- **Sense of Competence:** Sense of Competence in Dementia Care Staff (SCIDS) (28).
- **Attitudes towards People with Dementia:** Approaches to Dementia Questionnaire (ADQ) (29).
- **Job Satisfaction:** Minnesota Satisfaction Questionnaire, Short-form (30).

Baseline data for Usual ADLs – No Intervention

- Staff's usual reporting at the end of each shift.
- Additional: the survey webpage.
  - Subject name
  - Time: start of ADL and stop ADL
  - ADL checklist: toothbrushing, grooming, face wiping, taking medications
  - Was the activity completed?
- Subject's responses to the ADLs (multiple choice and text box)
  - Subject's autonomy to the activity (Likert scale of 1- 4)
  - Subject's attitude to the activity (Likert scale of 1- 4)
- At the end of the baseline studies, staff complete an ADCS-ADL score sheet for

each of their residents to provide longitudinal comparisons (31).

- Data collected during the Intervention phase

Reporting on The DevaWorld App's Feasibility (Aim 1)

- The DW app captures screen interactions, durations, end-of-session emoticons for self-assessment and end-of-session comments (choice of spoken or text input).
- The tablet's built-in camera records the dyad's expressions and exchanges during the session. These videos support analysis of engagement and reaction, and create a unique data set for developing speech emotion recognition system for future product upgrades.
- Occasionally research staff may also capture video and audio using an iPhone during DWS for capturing other nuances of the dyad engagement.
- In addition, at end of shift, staff complete a web-based questionnaire that
  - measures tolerance and acceptance of DevaWorld
  - records observations of resident's post and pre-post disposition
- Questions are a mix of multiple choice, 5-point Likert scales and free text
- Computers are located at the nurse station.

Reporting on Usual ADLs, following Intervention (Aim 2)

- Staff's usual reporting at the end of each shift.
- Additional: the survey website.
  - Subject name
  - Which ADLs were done (checklist)?
  - Time taken to start and finish
- Subject's responses to the ADLs (multiple choice and text box)
  - Autonomy to the activity (Likert scale of 1- 4)
  - Attitude to the activity (Likert scale of 1- 4)
- End of study
  - Residents will repeat Quality of Life and Response Behavior outcome measures (same ones as used in Baseline).
  - Participating staff will complete an ADCS-ADL scores sheet for each of their residents to provide longitudinal comparisons
  - Participating staff will undertake a 5 min exit interview at the conclusion of the trial. The interview will supplement and facilitate the interpretation of quantitative data gathered during including any post and pre-post concerns over the course of the study, which may provide further insights (32).

*iii. Explain training of individuals performing procedures*

Training sessions will take place after baseline studies as knowledge transfer before or during baseline may introduce a bias. Staff will be shown the DevaWorld app and how to work optimally with it.

This will be a hands-on lesson with staff sharing one device between them alternating staff and resident roleplays. Mentia's instruction guide, 'How to get the most out of your DevaWorld Session' and training videos will be the basis of the training. Staff will also be guided on environmental aspects such as the best time and place, how to set up and introduce the DWS, and how to transition from the session to the ADL.

Each site will have a highly-trained internal champion, who will attend training and provide on-going support to staff throughout the study

Agenda for group training session.

- Introduction to the study aims and their critical role.
- Instruction on DevaWorld usage with a focus on the ADL content.
- A short review to identify any knowledge gaps.
- Follow-up sessions will be scheduled as needed.
- Break
- Study Protocol covering consent, scheduling, reporting, risks
- 5-minute pre-intervention interview so that we can learn about any potential barriers to participation in, or adherence to, clinical trial requirements.

iv. *Be clear about the difference between what is standard (if there were no evaluation study) and what is done specifically for the study.*

As a single arm study, the distinction we believe the distinction will be clear, i.e., care shift with usual care and the intervention, and care shift usual care and no intervention.

During the 6-week intervention part of study; on both intervention and no-intervention days, staff are encouraged to modify their practice according to any insights they derive from the study. They will be asked to note any modifications in their end-of-shift report.

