- Following baseline and prior to the intervention phase, participating staff will take part in group training, with extra support as needed.
- During the intervention phase, a period of six weeks, the same dyads (or as close to same as is practical) will be assigned a schedule incorporating DWS followed by the same ADL routine as baseline.
- Each resident-participant will have two DWS per week. Staff-participants will spread this load across their shifts, averaging eight DWS sessions per 5-day week. We anticipate that session durations will average five minutes with variability according to resident-participants' individual interest levels on a given day. Staff schedule during study:

Mon 1h 10m	Tue 55m	Wed 1h 10m	Thu 55m	Fri 1h 10m
Res A DWS	Res A Mouth Care	Res A DWS	Res A Mouth Care	Res A Mouth Care
	Res B Mouth Care		Res B DWS	Res B Mouth Care
Res A Mouth Care	Res C DWS	Res A Mouth Care		Res C DWS
Res B DWS		Res B Mouth Care	Res B Mouth Care	
Res C Mouth Care	Res C Mouth Care	Res C Mouth Care	Res C Mouth Care	
Res B Mouth Care	Res D Mouth Care	Res D DWS	Res D Mouth Care	Res D DWS
Res C Mouth Care				
Res D Mouth Care		Res D Mouth Care		Res D Mouth Care
Reporting				

- Procedure for running a DWS

- **Initiating a session:**

Prior to the ADL, the dyad will sit in a quiet nook or the resident's bedroom with appropriate lighting. The care staff will ask the resident if they are comfortable (e.g. need a drink, need to go to the toilet, is comfortably dressed, has glasses and hearing aids in place).

To initiate the session, the care staff will open DevaWorld on the tablet device and invite resident to join.

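### A resident who asks to leave the study is offered sessions daily instead of twice a week and is withdrawn only after seven consecutive days of refusals

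*Combined protocol and SAP*

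**What the plan says.** All of the relevant text is in section VI.c.ii of the protocol.

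- **Normal frequency.** "Each resident-participant will have two DWS per week", with each staff member "averaging eight DWS sessions per 5-day week".
- **Declining a session.** Under Consent/No consent: "If no consent, the caregiver will reapproach in 3-5 minutes". After a second refusal that day's session is dropped and usual care begins.
- **Wanting to leave the study.** Under Ongoing Participation or Refusal, the trigger is a decision to stop being in the study at all, expressly distinguished from declining one day's session. The response is that "they will be offered DWS sessions daily". The end point is: "After 7 consecutive days of refusals, they will be withdrawn from the study".
- **Process consent.** Further down the same section, for a resident who no longer wishes, or is no longer able, to take part: "The staff observes residents wishes (verbally or non-verbally) to guide the next steps". Staff then tell the researcher. Depending on the situation, "it may or may not be appropriate to ask the resident again later".

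The sections on privacy and on safety monitoring refer to an attached DSMP and consent documents, which were not available for this review.

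**The concern.** The trigger and the response do not fit together. The trigger is a wish to leave. The response is more frequent contact, with enrolment continuing until a run of refusals is complete. Followed as written, a resident who wants to stop is approached more often than one who is content to carry on.

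Participant protection is what is at stake. The study population has moderate to severe dementia (section V.b), some residents take part through a proxy's consent, and the abstract names dignity, respect and choice as central themes of care. The rule gives staff no discretion to hold back an offer and gives the proxy no role. The process-consent text appears to point the other way, and nothing in the available text says which prevails.

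**Working it through.** The plan gives no figure for this rule, so the check is a count of contacts followed by a comparison of the two texts.

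**Inputs (all VI.c.ii):** two sessions per resident per week; a 5-day staff week; seven consecutive refusal days; a six-week intervention phase; one possible second approach per declined session.

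**Reproducing the schedule.** The table for the intervention phase can be read as sessions on Monday and Wednesday (Resident A), Monday and Thursday (B), Tuesday and Friday (C), and Wednesday and Friday (D). That is 4 residents × 2 = 8 sessions per 5-day week, which agrees with the stated average.

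**Offers after a wish to leave.**

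| Reading of the seven days | Offers under the rule | Sessions normally scheduled |
|---|---|---|
| 7 calendar days | at least 7 | 2 for every resident |
| 7 consecutive weekdays | at least 7 | 2 to 3, depending on resident and start day |

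For the weekday row, take Resident A. Starting on a Thursday, the seven weekdays contain one Monday and one Wednesday, so 2 sessions. Starting on a Monday, they contain two Mondays and one Wednesday, so 3. The other residents give the same range.

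**Approaches.** Assume the second approach after a few minutes also applies to each of these daily offers, which the text does not state. The rule then gives up to 7 × 2 = 14 approaches, against 2 × 2 = 4 if both scheduled sessions in 7 calendar days were declined.

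**Delay.** Seven calendar days are 7/42 = 17% of the six-week intervention phase.

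**The two texts side by side.**

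| | Seven-day rule | Process-consent bullets |
|---|---|---|
| Trigger | no longer wants to be in the study | no longer wants, or is unable, to be involved |
| Asking again | required, daily | depends on the situation; may be inappropriate |
| Who decides | fixed by the rule | guided by the resident's wishes |
| Stated scope | the study as a whole | use during sessions |

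The first three rows pull apart. The last allows the two texts to be reconciled, if process consent is taken to govern only what happens around a single session. Even on that reading, the extra offers and the delay remain, because they follow from the seven-day rule alone.

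**The case against.** The strongest reply is that the texts operate at different levels. Process consent is described as a method for use during sessions, and the sentence about asking again later runs straight on to the reapproach after a few minutes and the dropping of that day's session. So *later* can mean later the same day, with the seven-day rule alone governing exit from the study. This largely stands. A reader might infer a flat contradiction, but the documents support only an ambiguity. It is not removed entirely, because the bullets speak of a resident who no longer wants to be involved and of checking consent before a session, and every daily offer is such a check.

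It can also be said that wishes fluctuate in dementia, so some confirmation period is legitimate. That is fair. It supports asking once more, but not a higher rate of asking than for residents who have not objected.

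Third, there are safeguards. Any offer can be refused, passive disinterest counts as refusal, staff inform the researcher, and the research team reviews reports daily. These mean that no session is forced. They do not shorten the delay or reduce the offers.

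Two further inferences are tempting and should not be drawn:

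- **That one smile or nod restarts the count.** The protocol accepts "non-verbal consent (resident smiles/nods/leans toward the tablet/touches care staff in a positive way" and similar signs as the app opens. But refusal includes turning or looking away, which can follow, and consent is checked before, during and after a session. No text says how a mixed day is scored. Seven is a minimum; a reset is conjecture.
- **That the rule distorts the primary success criterion.** The Analysis Plan states the >55% threshold as a completion rate, whereas section V.d states it as a participation rate whose denominator is not defined. Delayed withdrawal could raise the first; extra refused offers could lower the second if offers were its denominator. The documents support no net size or direction.

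**Conclusion.** The point holds as a matter of participant protection. As written, a wish to leave the study produces at least 7 offers in place of 2 scheduled sessions over the same 7 calendar days, and enrolment continues meanwhile. This rests only on the literal text and the planned frequency; the figure of 14 approaches rests on the added assumption stated above. The relation to process consent is an unresolved ambiguity.

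The rule should be fixed, but it is not a defect that by itself invalidates the study. The protocol describes the study as minimal risk, sessions are planned at five minutes, and each can be refused. The wording may be a slip meant for repeated refusals of single sessions, though it says otherwise. The DSMP and consent form may already address the matter. If they do, the protocol text still needs to agree with them.

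**What to change.** Subject to IRB approval, replace the two sentences under Ongoing Participation or Refusal with:

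> If a resident expresses a wish to leave the study, and not only to decline that day's session, staff stop routine DWS offers and inform the researcher that day. Staff may ask once more, no later than the next normally scheduled session, only if appropriate under process consent. Unless the resident then agrees to continue, the resident is recorded as withdrawn from the date of the first request, and in any case within 7 calendar days; the proxy, where there is one, is informed. Refusing a single session is not withdrawal.

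The time limit is workable. On the schedule as read above, the gaps between a resident's sessions are 2 and 5 days (A and D) or 3 and 4 days (B and C), so the next scheduled session is never more than 5 days away.

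In the Analysis Plan (section IX), add that a resident withdrawn in this way before the end of week 8 is a non-completer. Check that the DSMP and consent form say the same.

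The cost is one amendment, one added sentence and a consistency check, with no new data collection. The downside is that a few residents whose refusal was temporary may be withdrawn earlier, which would slightly lower the completion rate.

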## VI. Privacy and Confidentiality

The attached DSMP and Informed Consent documents answer the following

- a. What steps will be taken to protect the subject's privacy?
- b. What steps will be taken to protect the confidentiality of the data obtained?
- c. Who will, or may in the future, have access to data?
- d. Is there a destruction date or event for identifiable data?

## VII. Safety Monitoring Plan

The attached DSMP and Informed Consent documents answer the following

- a. Definition of adverse events, serious adverse events
- b. What procedures will be used to monitor subject safety?
- c. Who will identify, document, and report adverse events?
- d. What is the frequency for review of summarized safety information and who will perform the review (e.g., safety monitoring board)?
- e. What are the stopping rules with regard to effectiveness and safety?

## IX. Analysis Plan

*Describe statistical analysis methods as appropriate. For example, will intention-to-treat methodology be used in the analysis? Will there be any sample stratification?*

- Thematic and sentiment analysis of tablet-recorded spoken and visual exchanges during DWS and post-session comments
- Statistical and text analyses of questionnaire responses
  - Statistical Analysis Plan
    - Assessment inventories with scores on the inventory's scale
    - Measuring mean value and standard deviation for the group
    - Complete a superiority statistical test
    - P-values calculated by t-test, 1 sided

HIPAA-compliant data capture software; eg REDCap, will be used to create the database and analyses. <https://www.project-redcap.org/>

Data will be reported graphically or with summary measure (e.g., means and standard errors or median and 95% confidence intervals), and subjected to statistical analysis when appropriate. Completion rates and grades scores will be presented as proportions and percentages.

ADCS-ADL scores will be compared from end of baseline to biweekly scores to the end of intervention and may be analyzed using a paired Student's t-test or the Wilcoxon signed-rank test if the data are not normally distributed.

Completion rates will be the percentage of all dyads who complete the entire eight weeks of study. The ratio of positively graded scores per dyad will be calculated to obtain the level of satisfaction of dyads and indicate the acceptability of DWS.

Aim 1: Successful primary outcomes are >55% completion rate and a statistically significant difference between assessments of completers and non-completers, indicating tolerability and acceptability of routine DWS.

Aim 2: The secondary outcome is to determine the feasibility of DevaWorld as an assistive tool for preparing and completing ADLs. Improved dyad outcomes are less time to complete ADLs, a reduction in negative response behaviors associated with the ADL, greater interest in the ADL, Care staff indicates tasks are easier than before.

Outcomes measures for baseline and intervention will be the same. As the score sheets cover a broader range of ADLs than those depicted in DW, overall and individual ADL scores will be analyzed and subjected to statistical tests. Our null hypothesis will be no statistical differences between ADL scores during the intervention and baseline phases

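### The ADCS-ADL comparison uses only residents with a later score, and loss is partly tied to declining DevaWorld, so it probably overstates the effect for all enrolled

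*Combined protocol and SAP*

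**What the plan says.** **Analysis.** For the timing, section IX (Analysis Plan) states: "ADCS-ADL scores will be compared from end of baseline to biweekly scores to the end of intervention". For the method, it says the scores "may be analyzed using a paired Student's t-test", or a Wilcoxon signed-rank test if normality fails. It leaves its own template question on intention-to-treat unanswered, defines no analysis set and gives no method for missing scores.

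**Collection.** Section VI.c.ii has staff complete an ADCS-ADL sheet at the end of baseline. The only later one is in the end-of-study list: "Participating staff will complete an ADCS-ADL scores sheet for each of their residents to provide longitudinal comparisons". The intervention-phase data list contains no biweekly ADCS-ADL.

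**Refusal and withdrawal.** In section VI.c.ii, refusing one session does not remove a resident: "If consent is not given a second time, the DWS will be dropped and the usual ADL routine will begin". The withdrawal rule concerns a resident who "decides that they no longer want to be involved in the study, not just the DWS session for the day". That resident is offered DWS daily, and then: "After 7 consecutive days of refusals, they will be withdrawn from the study". No ADCS-ADL is planned at or after withdrawal.

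**Numbers.** Section V.c gives a sample size of 32. Section VI.a raises it to 40 for 20% dropout. Section IX counts a completion rate above 55% as success for Aim 1.

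**The concern.** A paired test needs two scores from the same resident. Under the section VI schedule, anyone who leaves before the end of the study has no score after baseline and adds nothing to the comparison. One defined route out of the study runs through repeated refusal of the intervention, so part of the loss is linked to how the resident takes to DevaWorld.

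The study's hypothesis is that engaging with DevaWorld helps real ADLs. On that hypothesis, residents who decline it would be expected to gain less. Leaving them out would then raise the mean change and make a one-sided test easier to pass. The protocol intends the evidence to support a case for a credentialed digital therapeutic, so it matters whether the estimate describes everyone enrolled or only those who stayed.

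**Working it through.** **Inputs from the documents**
- 32 residents needed (V.c); 20% dropout and 40 enrolled (VI.a).
- Completion above 55% counts as success (IX).
- One-sided t-test (IX).

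**Assumptions, because the documents give no figure**
- Alpha 5% and power 80%.
- Leavers would have changed 0.5 SD less than stayers, in SDs of the change score.

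**1. The plan's own figure.** 32 / (1 − 0.20) = 40. This reproduces.

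**2. Largest loss that still meets the completion criterion.** 22/40 = 55%, which is not above 55%. 23/40 = 57.5%, which is. So up to 17 of 40 (42.5%) may be lost.

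**3. Size of the overstatement.** Mean in stayers minus mean in all enrolled = share lost × (stayer change − leaver change).
- 20% lost: 0.20 × 0.5 = 0.10 SD.
- 42.5% lost: 0.425 × 0.5 = 0.2125, about 0.21 SD.

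**4. Compared with what the test could detect** (exact one-sided paired t, each at its own sample size):

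| Retained | Overstatement | Detectable effect | Ratio |
|---|---|---|---|
| 32 of 40 | 0.10 SD | about 0.45 SD | 0.10/0.45 ≈ 22% |
| 23 of 40 | 0.21 SD | about 0.54 SD | 0.21/0.54 ≈ 40% |

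**5. How far the result depends on the assumption.** At 20% loss, with an assumed stayer change of 0.30 SD:

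| Leavers' change | All-enrolled mean | Overstatement |
|---|---|---|
| −0.30 SD | 0.18 SD | +0.12 SD |
| 0 | 0.24 SD | +0.06 SD |
| 0.30 SD | 0.30 SD | 0 |
| 0.45 SD | 0.33 SD | −0.03 SD |

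**6. Effect on the test.** The simulation sets the true mean change to zero and lets retention correlate with each resident's own change. Nominal false-positive rate is 5%.

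| Correlation | 32 of 40 retained | 23 of 40 retained |
|---|---|---|
| −0.3 | 1.4% | 0.5% |
| 0 | 4.9% | 5.0% |
| 0.1 | 7.3% | 9.3% |
| 0.3 | 14.7% | 24.9% |

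The correlation is unknown; the table shows only that a modest positive value matters.

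**The case against.** The strongest reply is that the withdrawal rule is narrower than it looks. It applies to residents who want to leave the whole study. Ordinary sessions run twice a week, and a resident who declines one stays in and receives usual ADL care. Persistent decliners who do not ask to leave can still have an end-of-study score. This stands. A reader might infer that the effect is estimated only in residents who like DevaWorld; the documents do not support that.

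Nor do the documents attribute the 20% dropout to refusal; illness, transfer or staffing could also contribute. This stands too. The illustration applies the 0.5 SD gap to every leaver. If half of them would have changed like stayers, it halves: 0.20 × 0.5 × 0.5 = 0.05 SD at the planned dropout.

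The paired test is tied to ADCS-ADL and is only a possible method. The other Aim 2 outcomes, such as ADL time and attitude, come from shift reports that exist up to withdrawal. So the point does not extend to Aim 2 as a whole. An uncommitted method does not, however, supply a plan for missing scores.

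A reader might also infer that Aim 1's comparison of completers with non-completers cannot be made without scores after withdrawal. That does not follow: baseline inventories and reports before withdrawal exist for both groups.

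Finally, a repeated-measures model assumes that missingness depends only on observed data, so it would not by itself cure loss driven by response to DWS. This is correct, and it is why the fix rests mainly on collecting scores and on a sensitivity analysis.

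**Conclusion.** The point holds for ADCS-ADL. As written, early leavers contribute nothing to that comparison, their loss is partly tied to declining the intervention, and sections VI and IX disagree on whether biweekly scores exist. The restriction to retained residents is implied by the paired test and the silence on missing data; the plan does not state it.

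It is tempting to say flatly that the effect is biased upward. The documents contain no data on ADL change in leavers, so upward is the plausible direction and not an established one. Under the assumed 0.5 SD gap, the overstatement is about a fifth of the detectable effect at the planned dropout and about two fifths at the largest loss that meets the completion criterion. Those ratios also rest on the assumed alpha and power. This should be corrected, but it concerns a secondary aim of a single-arm feasibility study and is cheap to repair.

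**What to change.** 1. Reconcile section VI.c.ii with section IX by adding the biweekly, staff-completed ADCS-ADL to the section VI schedule.
2. For residents who stop DWS but whose consent to data collection stands, keep collecting the ADCS-ADL at withdrawal and at week 8. Staff complete the form, so the resident need not use the tablet.
3. Define the analysis set as all enrolled residents. Replace the pairs-only test with a repeated-measures model on all available ADCS-ADL scores.
4. Add a sensitivity analysis that sets change to zero for residents without a later score.
5. Describe any result based on retained residents as exactly that, and report the number of withdrawals with reasons.

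The cost is analysis-plan wording and a short staff form every two weeks, which section IX already assumes. The estimate may be less favourable.
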